## 2. STUDY AIMS

The primary study objectives are as follows:

**Aim 1: Establish the feasibility of using mobile phones to follow up on hospitalized trauma patients after discharge in Cameroon.**

*Hypothesis:* Mobile phones are a feasible way of contacting trauma patients after they are discharged from the hospital in Cameroon.

We will contact trauma patients discharged from four hospitals participating in the Cameroon National Trauma Registry at intervals of two weeks, one month, three months, and six months following discharge. The response rate and decay of response over time will be tracked.

**Aim 2: Cross-validate a telephone-based triage tool to identify trauma patients who would benefit from further medical care.**

*Hypothesis:* A triage tool administered over the telephone can effectively identify injured patients who would benefit from further care for their injuries.

An over-the-phone triage tool will be used to predict a binary outcome two-weeks after discharge: needs further care or does not need further care. An independent physician blinded to triage tool outcome who will also render a determination on the same binary outcome, will examine those patients contacted by telephone. Physician assessment will be used as the gold standard to calibrate the model, which will be validated in a separate patient cohort.

**Aim 3: Characterize the impact of timely follow-up on long-term disability and socioeconomic consequences associated with trauma in Cameroon.**

*Hypothesis:* Trauma patients in need of post-hospitalization medical care will have improved disability outcomes if follow-up care is delivered promptly.

Patients will be given a modified Glasgow Outcomes Scale-Extended (GOSE) survey to complete at two weeks, one month, three months, and six months after hospitalization to quantify the death and disability associated with traumatic injury for each patient. Pre- and post-intervention results will be compared.

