**Implementation/Data Collection:** Patients contacted two weeks after discharge will be asked to give additional consent for participating in the triage tool part of the study. Those who consent will be contacted by research assistants and will answer 7-question survey. Patients whose responses trigger concern about the need for further medical attention will be informed that they should return to care and given appropriate instructions. All patients, regardless of triaged status, will be asked to schedule a time for a physical exam and will undergo one either at the hospital or in their place of residence. If patients return to the hospital, compensation for travel expenses will be provided on a sliding scale. This exam will occur within 1 week of the phone interview. Trained study physicians will conduct a structured, standardized exam that will ultimately culminate in a dichotomous outcome for “needs further care” or “does not need further care”. Based on the exam, the physician will determine if the patient would benefit from further services (including additional follow-up care, diagnostic or therapeutic interventions). Additional data will be collected regarding physician opinion as to whether the patient is demonstrating on-trajectory recovery for their age, health status, and injury, and whether the patient is at high, moderate, or low risk for a poor outcome. At the 2-week and 6-month time points, all contacted patients will be asked about their satisfaction with formal medical services, post-injury follow-up care, perceived convenience, and utility of mobile telephone follow-up.

**Figure 1: Step-wedge design of study.** For each site: Diagonal lines depict a GOSE baseline data collection phase, gray arrows depict intervention phase (1 year/site), and black blocks depict follow-up phase (6 months/site).

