##### b) Protections Against Risk

To protect and minimize against the unintentional disclosure of private health or identifying information: Patient data will be recorded on paper forms which will be stored in secure lock boxes at each of the hospital site for up to five years prior to local destruction. Trauma registry research assistants will enter data into the encrypted, password-protected, online database hosted on REDCap. All personnel with the potential to handle patient data (i.e. program manager, study investigators, field supervisors, RAs) will undergo standard protection of human data training and certification.

While the risk for physical and psychological discomfort are low, subjects will be informed that they are free to skip any survey questions that make them feel uncomfortable. To offset any financial risks that research participation will cause,

post-discharge trauma patients will be transferred mobile phone credits after any phone interviews conducted for the study. Subjects will be informed that their responses will be entered into an electronic database, which will be encrypted and password-protected. Subjects will also be informed that the data will be accessible only to research personnel.

It is highly unlikely that adverse effects will result directly from the study interventions. However, it is possible that during follow-up calls, patients may disclose information that suggests immediate need for medical or professional intervention. If subjects are suspected to have urgent medical or safety needs, research assistants will promptly report this information to the Cameroon-based Project Manager and [name] for adjudication. Where necessary, subjects will be re-contacted to urge them to seek medical care.

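### The Aim 2 reference physician is called blinded, but flagged patients know the triage advice before the exam and no step to prevent or record disclosure is described

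*Combined protocol and SAP*

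**What the plan says.** Section 2 (Study Aims, Aim 2) describes the reference standard as "An independent physician blinded to triage tool outcome who will also render a determination on the same binary outcome" and adds that "Physician assessment will be used as the gold standard to calibrate the model". The Protocol Summary and the study design list in section 3A also call the exam blinded.

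The procedure is under Approach, Aim 2, Implementation/Data Collection. At the two-week call, "Patients whose responses trigger concern about the need for further medical attention will be informed that they should return to care". No message to unflagged patients is described. Then "All patients, regardless of triaged status, will be asked to schedule a time for a physical exam", and "This exam will occur within 1 week of the phone interview". As to the exam itself, "Trained study physicians will conduct a structured, standardized exam", at the end of which "the physician will determine if the patient would benefit from further services".

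Two other places bear on who learns the triage result. Section 6b, on patients with suspected urgent needs, says: "Where necessary, subjects will be re-contacted to urge them to seek medical care". It sets no timing relative to the exam. Section 10 (Limitations) has the project manager alert investigators to subjects whose triage answers cause concern. It does not say whether examining physicians are outside that route.

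The Addendum states that triage calls with physician exams ran from February 2020 to August 2022, with pauses.

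**The concern.** Blinding is stated as a property of the reference standard, yet the procedure gives the flag's message to the person the physician is about to interview. A patient recently told to return to care has an obvious reason to say so. The protocol describes no request to withhold the advice, no check that the blind held, and no record of disclosure.

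Whether someone would benefit from further services is a judgement, and a physician who knows the advice may lean towards agreeing with it. The reference then partly contains the test it is meant to assess. Aim 2 is the aim the study is powered for. The 30% validation group comes from the same cohort and the same exam process as the training group, so validation would carry the bias forward and would not expose it.

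**Working it through.** The plan gives no disclosure rate and no accuracy for the tool, so there is no figure of its own to reproduce on this point. The 1300 target (13 variables × 10 participants ÷ 0.10 = 1300) reproduces and is unaffected.

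**Inputs**
- Prevalence of need: 50% (Addendum, multicentre preliminary data) and 13.7% (Aim 2 Sample Size, pilot). Both are rates of physician recommendation, used here in place of true need.
- True sensitivity 80% and specificity 70% for the flag given at the call: assumed.
- f, the share of flagged patients without need whom the physician labels as needing care because the advice became known: assumed 10%, 20%, 30%. This is disclosure multiplied by persuasion, not the disclosure rate alone.

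Only flagged patients are said to be told anything, so only false positives (FP) are moved, to true positives (TP). False negatives (FN) and true negatives (TN) stay as they are.

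**Formulas**
- Apparent sensitivity = (TP + f·FP) / (TP + f·FP + FN)
- Apparent specificity = TN / (TN + (1 − f)·FP)

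**Per 1,000 patients at 50% prevalence:** TP 400, FN 100, FP 150, TN 350.

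| f | Apparent sensitivity | Apparent specificity |
|---|---|---|
| 10% | 415/515 = 80.6% | 350/485 = 72.2% |
| 20% | 430/530 = 81.1% | 350/470 = 74.5% |
| 30% | 445/545 = 81.7% | 350/455 = 76.9% |

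**At 13.7% prevalence:** TP 109.6, FN 27.4, FP 258.9, TN 604.1. Apparent sensitivity is 135.5/162.9 = 83.2%, 161.4/188.8 = 85.5% and 187.3/214.7 = 87.2%. The specificities are the same as above, because prevalence cancels.

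**Opposite force.** Suppose a share h of flagged patients with true need receive care and no longer need it by the exam. They move from TP to FP. At 50% prevalence:
- h = 10%: sensitivity 360/460 = 78.3%, specificity 350/540 = 64.8%
- h = 20%: sensitivity 320/420 = 76.2%, specificity 350/580 = 60.3%

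**Why disclosed exams should not simply be dropped.** Suppose disclosure has no effect on the physician, and 30% of flagged patients disclose and are excluded. Then TP = 280 and FP = 105, so sensitivity = 280/380 = 73.7% and specificity = 350/455 = 76.9%. The exclusion alone turns 80/70 into 73.7/76.9, because it removes flagged patients selectively.

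**The case against.** The strongest reply is that the protocol has real safeguards. Everyone is examined whatever the triage result, so attending reveals nothing. The exam is structured and done by trained physicians. The call script and exam form are not reproduced, so silence in the protocol does not prove that disclosure went unrecorded. All of this stands. It narrows the concern without removing it: the patient can still reveal the advice, and the end point is still a judgement.

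A second reply is that the planned analysis refits a regression on the item answers and does not evaluate the flag. This also stands. Bias can enter only through the items that trigger the advice, so the 2×2 figures do not estimate the planned ROC or calibration results.

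A third is that the net direction is not settled. Care received between call and exam lowers apparent accuracy, as shown in the working.

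A reader might go further and infer any of the following, which the documents do not support:
- *Every patient learns a triage result.* Only flagged patients are said to be advised. Absence of advice may be informative, but nothing supports moving false negatives to true negatives at the same rate as false positives to true positives, which would overstate the gain in sensitivity.
- *The rise from 13.7% to 50% recommended for care shows leakage.* The Addendum attributes it to more severe injuries at added sites and to selection bias. Under the assumed 70% specificity, relabelling every flagged patient without need would raise 13.7% only to 13.7 + 0.30 × 86.3 = 39.6%.
- *The blind was in fact broken.* No document reports that.

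**Conclusion.** The concern holds as a limited design weakness. Blinding is asserted, but flagged patients carry the advice into an exam that ends in a judgement, and the protocol describes no step to stop or record disclosure.

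Disclosure, taken by itself, would tend to inflate apparent accuracy. For the flag, under the assumed 80/70 and 50% prevalence, the gain is about 0.6 to 1.7 points of sensitivity and 2.2 to 6.9 points of specificity for relabelling of 10% to 30%. At 13.7% prevalence the gain in sensitivity is larger, 3.2 to 7.2 points. These sizes rest on assumed accuracy and assumed relabelling, do not transfer directly to the refitted item model, and could be offset by care received before the exam. The net bias therefore cannot be signed from the documents. The point is minor in severity, and its actual size is unknown.

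**What to change.** Leave the advice to patients as it is.

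**For any remaining or future exams**
- Add one line to the call script asking patients not to mention the call result until the physician has recorded the determination.
- Add one exam-form field, completed after the determination: did the physician learn the triage advice, yes or no.
- Keep all exams in the accuracy estimates. To look for influence, compare the share judged to need further care by disclosure status, among flagged patients only and adjusting for the item answers.

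**For exams already completed without this record** (the Addendum dates them to August 2022), only the reporting can change. State that the physician was intended to be blinded, that flagged patients knew the advice, and that the protocol documents no record of disclosure. Say that disclosure specifically would tend to inflate apparent accuracy. Do not claim that physicians were uninformed by study staff unless the sponsor can confirm that examiners were outside the alert route in section 10.

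**Cost:** one script line, one form field and one supplementary comparison; for completed exams, wording only. The sample size does not change. Self-reported disclosure is imperfect, and the comparison is observational: patients with more worrying problems may be likelier to mention the advice.

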**Triage Tool Development:** Our extensive literature search for existing telephone-based follow-up triage tools for injured patients yielded no directly applicable studies conducted in LMIC settings. A few non-trauma related instruments were developed for HIC and LMIC settings. The one most relevant to our proposed project was a post-operative tool used to follow-up on elective surgery patients in an industrialized country setting. The lack of studies investigating mobile phone follow-up for trauma patients in LMICs led us to review mobile-based follow-up approaches in other fields of medicine and surgery in both HIC and LMIC. Based on this review, we generated a list of potential questions aimed at identifying post-injury individuals in need of further care and modified the questions to reflect relevance to the Cameroonian context. Potential questions were also solicited from local experts, including surgeons and physicians who take care of injured patients in Cameroon. All potential questions from both sources were compiled and reviewed by an expert panel of Cameroonian medical care providers. Redundant questions were combined and refined; ambiguous questions were revised. Any questions found to be non-essential or marginally contributory were removed. The resulting preliminary triage tool consisting of 7 questions (Figure 1) was then pre-tested for acceptability and understandability on a small group of hospitalized patients and family members. In preliminary testing, of 150 triaged patients, 20 (13%) tested as needing further care. The triage tool will be administered via mobile-phone by trained research assistants as described in Aim 2.

Table 1: Questions included in the mobile-phone based triage tool		
#	Question	Answers
1	Is the patient currently alive?	 Yes  No: Date of Death: _____ * Stop interview
2	Since leaving the hospital how have they been feeling?	 Much better  Somewhat better  The same as when I left the hospital  Sicker  Much sicker
3	Have they been able return to usual daily activities?	 Yes  They have returned to some activities, but they are harder and/or require extra help to do them  No

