## Primary Outcomes

mHealth triage tool score; physician exam determination for “needs further care” or “does not need further care”.

**Sample Size:** The preliminary triage instrument has 13 variables derived from 7 questions. A minimum sample size of 10 participants per variable per potential model outcome (either needing further care or not needing care) is required to adequately power regression analysis. Our preliminary data suggests that physician exams leading to a recommendation for further care occur for 13.7% of calls. Conservatively estimating that 10% of contacted patients will require further care, a sample size of 1300 patients in the triage cohort will be targeted.

**Data Analysis:** Data from the prospective cohort will be divided into training and validation groups (70% and 30% of the overall cohort respectively). Stepwise multiple regression with bidirectional elimination will be used on the training group dataset to build the best model for predicting physician recommendation for further care (considered as a binary outcome). Survey questions that are found not to contribute significantly to prediction will be dropped from the final triage tool. The resultant model will be applied to data from the validation cohort. To establish predictive accuracy, we will assess calibration of the model by comparing the mean error between the predicted risk and actual physician response in this cohort. Receiver operating characteristic (ROC) curves will be calculated to evaluate the discrimination of the model. As the consequences of a false-positive survey leading to unnecessary patient follow-up are minimal, whereas false-negatives may result in poor health outcomes, risk cutoffs will target a highly sensitive test with minimal false negatives. Ratings of telephone follow-up acceptability will be aggregated and summarized.

**Aim 3: Characterize the impact of timely follow-up on long-term disability and socioeconomic consequences associated with trauma in Cameroon.**

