Adhering to local and national guidelines in Cameroon, we temporarily suspended all follow-up physician exams of discharged trauma patients to prevent direct contact between patients and research staff, as well as to reduce patient exposure during travel. Consequently, we were forced to delay the implementation of our intervention (telephone-based triage tool) at all sites due to a lack of capacity to cross-validate triage results with physician assessments. Physician exams (Aim 2) had been initiated only one month prior to this suspension at our first partner hospital site in accordance with our step-wedge study design. We resumed all research activities in September 2020, after the Cameroonian Ministry of Public Health had established protocols for COVID-19 control and prevention in the workplace, and our team could reliably supply personal protective equipment for all research staff. Patient recruitment in our intervention cohort was thus delayed for a total period of six months. COVID-19 impacted patient recruitment and we applied for a 12-month funded supplement to enable us to accrue a sample size enough to validate our tool.

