*Supplement Sample Size Calculations Adjustment:* Data collected from our prospective cohort will be divided into training and validation groups (70% and 30% of the overall cohort respectively). Our original sample size was calculated to account for a conservative prevalence of 10% of contacted patients needing further follow-up care. Based upon detecting a significant departure from 50% specificity, we estimate that we would require approximately 400 patients who are not recommended for follow-up care to be included in our validation sample. We will therefore target a sample size of 1330 trauma patients in our triage cohort. New multicenter preliminary data, however, suggest that physician exams leading to a recommendation for further care occur for 50% of contacted patients. This is a significant deviation from prior single-institution Cameroon pilot data that estimated 13.7% of contacted trauma patients would need further care. The inclusion of additional hospital sites that receive patients with more severe injuries as well as selection bias are likely contributing to this difference. If our preliminary findings remain consistent, we anticipate only requiring 220 patients not recommended for follow-up care to be included in our validation sample and 730 patients to be targeted in our triage cohort. Using a conservative estimate for our sample size calculation approach enables us to create a buffer and ensure our study is adequately powered to achieve statistical significance.

Triage tool was administered at 2 weeks with physician examination assessments from February 2020 till August 2022 (with the pauses noted above). Final 2 weeks follow-up was completed on September 14, 2022.

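### Does the lack of a rule for triaged patients who miss the physician exam undermine the triage tool's sensitivity, specificity and cut-off?

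*Combined protocol and SAP*

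**What the plan says.** In the protocol's Approach section, Aim 2 (Implementation/Data Collection), the seven-question tool is given by telephone two weeks after discharge. The plan then says: "All patients, regardless of triaged status, will be asked to schedule a time for a physical exam and will undergo one". The exam is at hospital or at home, within a week of the call, and travel to hospital is compensated. In the same paragraph, "Patients whose responses trigger concern about the need for further medical attention will be informed that they should return to care". Question 1 of the tool ("Is the patient currently alive") ends the interview if the patient has died.

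The Data Analysis text under Primary Outcomes splits the cohort 70/30 and builds a stepwise model for the physician's determination. It continues: "The resultant model will be applied to data from the validation cohort". Calibration and ROC curves follow, and "risk cutoffs will target a highly sensitive test with minimal false negatives".

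The Addendum reports that exams were suspended during the pandemic and the tool was delayed at all sites "due to a lack of capacity to cross-validate triage results with physician assessments". Its revised sample size is "Based upon detecting a significant departure from 50% specificity". It also notes that need for care was running at 50% rather than the pilot's 13.7%, and says that the added sites as well as "selection bias are likely contributing to this difference".

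The Limitations section requires quarterly written reports on enrollment against target, demographics and retention, overall and by site.

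**The concern.** The model, the ROC curve and the cut-off can use only patients who have a physician determination. Attendance is voluntary, and only patients whose answers raise concern are told to return to care, so attendance could differ by triage result. That is the setting for verification bias: if flagged patients are examined more often, sensitivity reads too high and specificity too low, and the signs reverse if they are examined less often. The plan names no analysis set, no handling of missed exams and no comparison of examined with unexamined patients. The Addendum mentions selection bias without saying at which step it arose.

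At stake would be the two quantities that Aim 2 relies on most: a cut-off meant to leave few false negatives, and a specificity that the supplement sample size compares with 50%.

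**Working it through.** **Inputs from the documents.** 13 candidate variables, 10 participants per variable per outcome and 10% planned need (Primary Outcomes, Sample Size); 20 of 150 pilot patients, 13.3%, triaged as needing care (Triage Tool Development); 13.7% pilot need and 50% later need (Addendum). Attendance and accuracy are not given and are assumed below.

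**The plan's own figure.** 13 × 10 / 0.10 = 1300, which reproduces. It has no allowance for missed exams.

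**Formulas.** Let r be attendance in flagged patients divided by attendance in unflagged patients, with attendance unrelated to need once the flag is known.
- Reported sensitivity = Se·r / (Se·r + 1 − Se)
- Reported specificity = Sp / (Sp + (1 − Sp)·r)

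**The plan as written.** Everyone is examined, so r = 1 and both formulas return the true values. The same holds at any equal attendance below 100%.

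**An assumed departure, true values 90% and 60%, flag equal to the final cut-off.**
- r = 1.25: 1.125/1.225 = 91.8% and 0.6/1.1 = 54.5%.
- r = 0.8: 0.72/0.82 = 87.8% and 0.6/0.92 = 65.2%.
- r = 1.25 requires attendance of at most 1/1.25 = 80% in unflagged patients.

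The refitted cut-off need not equal the flag. If a positive result is 50 points more common in flagged than in unflagged patients with the same need, the bias halves: 90.9% and 57.3% at r = 1.25, 88.9% and 62.6% at r = 0.8. On a binormal model the ROC area moves from 0.861 to 0.856 or 0.865.

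**Effect on a cut-off tuned to read 90% sensitivity** (flag nested in the score). At r = 1.25 true sensitivity is 0.9 × 1.225 / 1.25 = 88.2%. At r = 0.8 it is 0.9 + (0.9 × 0.82 − 0.72) = 91.8%.

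**The pilot flag rate gives a different picture.** At 90/60% and 13.7% need, the share flagged would be 0.137 × 0.9 + 0.863 × 0.4 = 47%, against 13.3% in the pilot. Hold 13.3% flagged, 13.7% need and 90% sensitivity instead. Flagged without need is 0.1333 − 0.1233 = 0.0100, so specificity is 1 − 0.0100/0.863 = 98.8%. At r = 1.25 the shifts are +1.8 points in sensitivity and −0.3 in specificity. With 50% sensitivity they are +5.6 and −1.7. Which measure suffers more therefore depends on the accuracy assumed. The two pilot percentages may come from different samples, and the flag rule is not defined, so this is a second scenario and not an estimate.

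**Could attendance explain 50% need?** If only flagged patients were examined, need at 90/60% would be 0.1233 / (0.1233 + 0.3452) = 26%. At the pilot flag rate it passes 50% once sensitivity exceeds 0.5 × 0.1333 / 0.137 = 49%. The documents neither establish nor exclude this explanation.

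**Would a pre-specified correction help?** Simulation with 399 validation patients (30% of 1330), 90/60% accuracy and the flag as the test gives these root-mean-square errors in points, Begg-Greenes corrected against uncorrected:

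| Need | Attendance, flagged/unflagged | Sensitivity | Specificity |
|---|---|---|---|
| 10% | 90%/60% | 6.0 vs 5.4 | 2.6 vs 10.5 |
| 10% | 90%/72% | 5.6 vs 5.0 | 2.6 vs 6.2 |
| 10% | 72%/90% | 5.2 vs 6.5 | 2.7 vs 5.9 |
| 50% | 90%/60% | 2.6 vs 3.7 | 3.6 vs 10.8 |
| 50% | 90%/72% | 2.4 vs 2.8 | 3.6 vs 6.7 |

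Specificity gains whenever attendance is unequal. Sensitivity loses at the planned 10% need when flagged patients attend more, which is the direction that advice to return to care would suggest. Inverse-probability weights and correction of a refitted cut-off were not simulated.

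**The case for a change.** The best argument for a change is that a statement that all patients will undergo an exam is an intention. Some people will not attend, and one group receives advice that the other does not. At r = 1.5, for example 90% against 60% attendance, a true specificity of 60% would read 0.6/(0.6 + 0.4 × 1.5) = 50%, exactly the reference value in the Addendum. Tabulating attendance by triage result costs almost nothing, uses data already held, and remains possible although exams ended in August 2022.

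Part of this stands. The plan has no contingency rule, complete verification is not demonstrated, and the quarterly reports are not split by triage result. What does not stand is the step from there to a defect in the plan. The design removes the bias at its source through exams for everyone, home visits and travel compensation. When exams had to stop, the study delayed the tool rather than collect unverified triage results. The large specificity shift needs both a wide attendance gap and a low specificity that fits poorly with the only flag rate the documents give. Deaths found at question 1 leave no further triage answers, so those patients could not enter the model anyway.

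**Conclusion.** No change to the plan follows. It omits a detail about departures from a design that, followed as written, has no verification bias. The sizes are conditional. At an attendance ratio of 1.25 they run from +1.8 and −0.3 points (sensitivity and specificity, pilot flag rate, 90% sensitivity assumed) to +1.8 and −5.5 points (90/60% assumed). They are zero if attendance is equal, and reverse in sign if flagged patients attend less. All of this assumes that attendance depends only on the triage result. In that case the fitted risks are unbiased, and the cut-off is affected only because it is chosen by sensitivity.

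An analyst will need to count triaged and examined patients to define the analysis set, and tabulating those counts by triage result and site would show any imbalance. Only a material imbalance would justify corrected values beside the uncorrected ones, with the caution that correction can increase the error in sensitivity when need is low. That judgement can be made once the counts are known.
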